1.1. Historical Background of Metastatic Lung Cancer

The first surgical resection of a pulmonary metastasis (sarcoma) dates back to 1882 and is credited to Weinlechner. Barney and Churchill performed the first isolated resection of a pulmonary metastasis in the United States in 1939. In the past 25 years, surgical resection has become widely accepted for the treatment of pulmonary metastases.²¹

Today, lung cancer is the most frequent malignancy causing death in the world. Common primary tumors that usually present as lung metastasis are breast, colon, kidney, uterus and cervix, prostate, and head and neck tumors. Though surgery, with or without systemic chemotherapy, remains the treatment option of choice, not all patients are considered appropriate candidates for this treatment option.²² Therefore, it is necessary to develop alternative, less invasive treatments for patients who are not candidates for surgery.

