1.2. Metastatic Lung Cancer Treatment Options

The choice of treatment depends mainly on the type of lung cancer and its stage. Treatment may include surgery, chemotherapy, radiation therapy, targeted therapy, or a combination of treatments, depending on the stage and size of the tumor. Treatment may be local or systemic.²³

Surgery is typically the best option with localized disease (no mediastinal invasion), however only 25% of tumors are suitable at the time of diagnosis for potential curative resection. Chemotherapy and/or external beam radiation (XRT) with chemotherapy is generally the standard treatment for regional disease. If the primary malignancy is controlled and there is no evidence of extrathoracic disease, then resection may be considered. Besides the traditional treatment options, minimally invasive treatment options include stereotactic radiotherapy, brachytherapy, bronchial arterial infusion of chemotherapy, photodynamic therapy and thermal ablation. Ablative technologies that are emerging as treatment options for lung cancer tumors include radiofrequency, microwave and cryoablation. ²²

CUC10-LNG06-04 Page 6 of 38

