
CUC10-LNG06-04 Page 7 of 38

the endobronchial element of the tumor and recanalization of the tracheobronchial obstruction. The removal of this obstruction accounts for the improvement in dyspnea and lung function tests, which are vital to the alleviation of symptoms in those with lung cancer due to the poor prognosis of this disease.²⁶

Kawamura et al reported a series of 35 tumors in 20 patients treated with cryosurgery for metastatic pulmonary tumors. Criteria for treatment included tumors < 3cm, less than 5 metastatic tumors, life expectancy greater than 1 year, absence of active extrapulmonary metastasis, Eastern Cooperative Oncology Group scores of 0 to 1, definitive pathologic diagnosis or obvious clinical features, and normal coagulability. CT guided cryoablation was performed with a 2 or 3 mm diameter cryoprobe (Endocare, Inc.) with 2 cycles of 5 minute freezing followed by a third cycle of 10 minute freezing to make an iceball of 2.5 to 3.0 cm in diameter. Local anesthesia was used in all cases. The primary endpoint of this study was the early outcome and feasibility of cryoablation for metastatic tumors < 3 cm. The secondary endpoint was tumor control. The mean age of patients was 57 years old. Two of the 20 patients underwent cryoablation twice due to bilateral metastasis, resulting in a total of 22 cryosurgery sessions. Pneumothorax occurred in 11 of 22 treatment sessions. Seven cases of pleural effusion, 8 cases of hemoptysis, and 1 case of phrenic nerve palsy were reported. The mean hospital stay was 2.6 days.

There were no treatment related deaths or conversion to surgical intervention. Response Evaluation Criteria in Solid Tumors (RECIST) was applied to assess change in tumor mass post-operatively. Two patients had complete response, 8 had partial response, 8 had stable disease, and 2 had progressive disease, thus resulting in a 50% response rate. The overall tumor recurrence rate was 54.3%. The median follow-up was 21 months for 18 patients. During the 9-12 month period, 7 of the 18 patients developed a local recurrence of 7 (20%) of tumors in 7 (35%) patients. Five patients underwent additional cryosurgery without complication or local recurrence. Pneumothorax was reported in 50% of the cases, 27% experienced pleural effusion, 41% hemosputum, and 4.5% phrenic nerve palsy. The Kaplan Meier 1-year survival was 89.4%.²⁷

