5.3. Other Endpoints

Other endpoints for this study include, but are not limited to:

- Assessing overall disease specific survival at 3, 6, 12, 24, 36, 48 and 60 months post cryoablation.
- Assessing time to disease recurrence or progression.
- Assessing the changes in physical function and quality of life over time. (See Section 11.5.4)
- Assessing cryoablation technical success. (See Section 11.5.4)

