7.2. Inclusion Criteria

Eligible patients for this study must meet all of the following criteria:

- 7.2.1. Patient must be at least 18 years old.
- 7.2.2. Patient has signed a written informed consent.
- 7.2.3. Patient presents with Stage 4 pulmonary metastatic disease with metastatic disease previously confirmed by prior biopsy; or
 Patient presents with Stage 4 pulmonary metastatic disease previously confirmed on
 - Patient presents with Stage 4 pulmonary metastatic disease previously confirmed on imaging (e.g. CT or MRI) with known (biopsied) primary disease.
- 7.2.4. Patient has up to 3 local metastases unilaterally targeted by cryoablation. (treatment in both lungs must be on separate treatment days) Maximum number of pulmonary tumors bilaterally per patient will be 5 total pulmonary tumors.
- 7.2.5. Targeted tumor(s) defined as intra pulmonary or pleural with a maximum size of 3.5 cm.
- 7.2.6. The target tumor is determined (by CT/MRI images) to be in a location where cryoablation is technically achievable based on the proximity of adjacent organs and structures.
- 7.2.7. ECOG performance status of 0-2.
- 7.2.8. Karnofsky Performance Scale (KPS) score ≥60.
- 7.2.9. Platelet count >50,000/mm³ within 60 days prior to study treatment.
- 7.2.10. INR < 1.5 within 60 days prior to study treatment.
- 7.2.11. Patient has a life expectancy of >3 months.
- 7.2.12. Patient is clinically suitable for cryoablation procedure.

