7.3. Exclusion Criteria

Patients not eligible for participation in this study include patients who have any of the following:

- 7.3.1. Patient's primary cancer is lung cancer.
- 7.3.2. Patient is unable to lie flat or has respiratory distress at rest.
- 7.3.3. Patient has uncontrolled coagulopathy or bleeding disorders.
- 7.3.4. Patient has had chemotherapy with neutropenia to levels (ANC <1000) that produce increase risk for the cryoablation procedure.

- 7.3.5. Patient has a history of an allergic reaction to iodine injections or to shellfish.
- 7.3.6. Patient has evidence of active systemic, pulmonary, or pericardial infection.
- 7.3.7. Patient has a debilitating medical or psychiatric illness that would preclude giving informed consent or receiving optimal treatment or follow up.
- 7.3.8. Patient is currently participating in other experimental studies that could affect the primary endpoint.

CUC10-LNG06-04 Page 12 of 38

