11.5.4. Other Endpoints

Technically successful treatment definition

A technically successful treatment will be defined by an ablation volume encompassing the tumor with at least a 5 mm margin.

Technical success will be calculated on a per tumor level as well as a patient level. To be considered a technical success on a patient level all tumors treated during the baseline procedure must meet the technical success criteria.

Disease recurrence or progression definitions

Disease recurrence or progression will be determined locally by evidence of an increase in tumor size and/or contrast enhancement.

Disease-specific survival rate is defined as the time in days from cryoablation procedure to death due to lung cancer. Patients who are alive will be censored at the date of their last visit. Patients who have died from causes other than lung cancer will be censored at the time of death. Disease-specific survival rates will be summarized by using Kaplan-Meier methodology.

Overall survival rate is defined as the time in days from cryoablation procedure to death. Patients who are alive will be censored at the date of the last visit. Overall survival rates will be summarized by using Kaplan-Meier methodology.

Time to recurrence is defined as the time in days from cryoablation procedure to disease recurrence or progression. Patients without disease recurrence or progression will be censored at the date of their last visit or their date of death (due to any cause). Recurrence free survival rates will be summarized by using Kaplan-Meier methodology.

Intra-procedural data

Initial cryoablation procedure information including the type of procedure, tumor size and number, cryoablation needle type and the number of each type of needle used, freeze and thaw times, method of thaw (active or passive), and ice formation and how it encompasses the tumor will be summarized.

Physical performance and quality of life

Physical performance (ECOG and KPS) and quality of life (SF-12) assessments will be made by examining the change in the baseline scores to those reported post-operatively as defined in Sections 9.3.1 and 9.5, respectively.

CUC10-LNG06-04 Page 20 of 38

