#### Disease recurrence or progression

Disease specific survival, overall survival, and time to disease recurrence or progression will be analyzed by Kaplan-Meier methodology. These measures are defined as:

**Disease-specific survival** will be analyzed as the time in days from cryoablation procedure to death due to lung cancer. Patients who are alive will be censored at the date of their last visit. Patients who have died from causes other than lung cancer will be censored at the time of death.

**Overall survival** will be analyzed as the time in days from cryoablation procedure to death. Patients who are alive will be censored at the date of the last visit.

Freedom from disease recurrence or progression will be analyzed as the time in days from cryoablation procedure to disease recurrence or progression, determined locally by evidence of an increase in tumor size and/or contrast enhancement. Patients without disease recurrence or progression will be censored at the date of their last visit or their date of death (due to any cause).

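### Disease-specific survival counts only deaths from lung cancer, yet patients with a lung primary are excluded, so the event does not match the enrolled disease

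*SAP*

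**What the plan says.** Protocol 5.3 lists the endpoint among the other endpoints: "Assessing overall disease specific survival at 3, 6, 12, 24, 36, 48 and 60 months post cryoablation". The SAP (Supportive Endpoint Analyses, Disease recurrence or progression) measures it as "the time in days from cryoablation procedure to death due to lung cancer", using Kaplan-Meier methods. Protocol 11.5.4 defines it the same way and adds: "Patients who have died from causes other than lung cancer will be censored at the time of death". The SAP repeats that censoring rule. Overall survival is defined separately in both places and counts every death.

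On who is enrolled, Protocol 7.2.3 gives two routes. The first is "Patient presents with Stage 4 pulmonary metastatic disease with metastatic disease previously confirmed by prior biopsy"; the second is Stage 4 pulmonary metastatic disease confirmed on imaging with a biopsied primary. Exclusion 7.3.1 reads: "Patient's primary cancer is lung cancer".

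Neither document defines lung cancer for this endpoint. Neither says who assigns cause of death or how an unknown cause is classed.

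**The concern.** The event names the one cancer that the eligibility criteria exclude. Applied as written, the rule turns deaths from metastatic colon, breast or kidney cancer into censored observations. Those are the deaths a disease-specific curve is meant to show.

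A looser reading does not settle the matter. The term could mean only the metastases in the lung, or the whole Stage 4 malignancy. The listed eligibility criteria do not exclude extrapulmonary disease, and the SAP (Additional Data Summaries, Disease status) plans to summarise additional metastatic disease found during the study. Deaths from the primary or from spread outside the lung can therefore be expected, and nothing says whether they are events.

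At stake is a named survival endpoint at seven time points. The same deaths would give different curves depending on how one term is read at each site. Protocol 11.2 says the data will help choose endpoints for a pivotal study, although no section says disease-specific survival will be used to size it.

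**Working it through.** **Text check.** There are three possible readings.

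1. *Literal (a lung primary).* Almost no death qualifies. The exceptions are a new lung primary, or an ineligible patient who was treated and kept in the ITT population. The SAP allows about 10 extra patients for those who do not meet the criteria.
2. *The lung metastases.* Deaths from the primary or from extrapulmonary spread are left unassigned.
3. *The enrolled Stage 4 cancer.* All deaths from that cancer count.

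The endpoint list, the abbreviations, the safety definitions and the rest of the SAP do not choose between them. Protocol 14 requires recording of adverse events only within 30 days of the procedure. Safety assessments run to Month 60 and sites are asked to document outcome (Protocol 6.4), so cause of death may be captured on forms not in the file, but no attribution rule is stated.

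**Illustration of size.** The plan gives no disease-specific rate to reproduce. Assume proportional cause-specific hazards. Let c be the share of deaths due to the study cancer and f the fraction of those recorded as lung cancer. Then

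DSS = OS^(c × f).

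Inputs:
- OS at 1 year: Protocol 3.2, for a 20-patient pulmonary-metastasis series, "The Kaplan Meier 1-year survival was 89.4" percent.
- OS at 60 months: not in the documents; 30%, 50% and 70% assumed.
- c = 0.90: assumed, varied from 0.80 to 1.00.
- f = 1 (reading 3), 0.5 (assumed) and 0 (literal).

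For example, at 1 year 0.894^0.90 = 0.904 and 0.894^0.45 = 0.951. At OS 50%, 0.50^0.90 = 0.536 and 0.50^0.45 = 0.732.

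| OS | f = 1 | f = 0.5 | f = 0 | Gap, f = 0.5 minus f = 1 | Gap for c = 0.80 / 1.00 |
|---|---|---|---|---|---|
| 89.4% (1 year) | 90.4% | 95.1% | 100% | 4.7 points | 4.2 / 5.2 |
| 70% (60 months) | 72.5% | 85.2% | 100% | 12.6 points | 11.5 / 13.7 |
| 50% (60 months) | 53.6% | 73.2% | 100% | 19.6 points | 18.4 / 20.7 |
| 30% (60 months) | 33.8% | 58.2% | 100% | 24.3 points | 23.6 / 24.8 |

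Expected 1-year deaths are 30 × 0.106 = 3.2 to 40 × 0.106 = 4.2.

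The result depends far more on f than on c. At OS 50% and c = 0.90, f = 0.9 gives 0.50^0.81 = 57.0% (+3.4 points) and f = 0.75 gives 0.50^0.675 = 62.6% (+9.0 points).

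**Readings 2 and 3 compared.** Split deaths into lung metastases / other cancer / non-cancer as 20/70/10, 50/40/10 or 30/40/30 (all assumed). Reading 2 is OS raised to the first share; reading 3 is OS raised to the sum of the first two. At OS 30% with 20/70/10, the values are 78.6% and 33.8%, 44.8 points apart. At OS 70% with 50/40/10, they are 83.7% and 72.5%, 11.2 points apart. Across the three splits and three OS values the gap is about 11 to 45 points.

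**The case against.** The strongest reply is that nobody would apply the literal reading. The endpoint is called disease-specific, which points to the disease under study, and the protocol uses the term loosely. Under its heading on treatment options for metastatic lung cancer it says "The choice of treatment depends mainly on the type of lung cancer and its stage", and the preceding background section says "Common primary tumors that usually present as lung metastasis are breast, colon, kidney, uterus and cervix, prostate, and head and neck tumors". Protocol 3.3 also passes from lung cancer to pulmonary metastatic disease without distinguishing them. If everyone reads the term as the enrolled cancer, the inflation is zero.

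That is the likely intent, but it is an inference. Within the plan's own rules, the only other use of the term is exclusion 7.3.1, where it means a lung primary. Protocol 3.2, in describing a 187-patient series, also separates primary lung cancer from metastasis. The choice between readings 2 and 3 would remain open in any case.

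The objection to the numbers largely stands. The value f = 0.5 has no source, and the 60-month survival figures are assumed. The 1-year figure comes from a more selected series: life expectancy over 1 year, ECOG 0–1, tumors under 3 cm and no active extrapulmonary metastasis. This trial accepts life expectancy over 3 months, ECOG 0–2, tumors up to 3.5 cm and, on the listed criteria, extrapulmonary disease. The percentages show that the choice of reading can decide the result; they do not predict it.

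It is also fair to say that a sponsor testing a local lung treatment might intend the narrower reading 2. If so, the plan has to say so.

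**Conclusion.** The concern holds. The event and censoring rule are wrong as written for this population: followed literally, they censor nearly every death from the enrolled cancer. That mismatch is certain and appears in both documents.

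The numerical effect is uncertain. It ranges from nothing, if the enrolled-cancer reading is applied throughout, to a curve fixed near 100% under the literal one. With half of the study-cancer deaths recorded as lung cancer, and 90% of deaths due to that cancer, disease-specific survival rises by about 5 points at 1 year and 13 to 24 points at 60 months, on the assumed survival figures.

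The consequence is bounded. The endpoint is supportive, the study is descriptive and unpowered, the efficacy endpoint is local tumor control, and overall survival does not depend on the definition. It should be fixed, but it does not threaten the main result.

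**What to change.** In Protocol 11.5.4 and in the SAP, define the event as death due to the patient's primary malignancy or its metastases at any site, and censor deaths from other causes. This is the ordinary meaning of disease-specific survival for patients with metastatic disease. If the sponsor intends a narrower event, such as death from the lung metastases only, it should say so and state how deaths from the primary and from extrapulmonary spread are handled.

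As a secondary step, state who assigns cause of death and from what source through Month 60, and how unknown-cause and procedure-related deaths are classed.

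The cost is one definition sentence and one attribution rule in each document. A cause-of-death field may be needed if the case report forms lack one. Vital-status follow-up after withdrawal may also be needed, because Protocol 6.2 withdraws patients who require further local treatment to an index tumor. No extra patients are required. The reported rate may look less favourable than under the literal wording; it will not change if the enrolled-cancer reading is already in use.

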6.4. Patient Withdrawal

Patients may withdraw from this study at any time, with or without a reason, without prejudice to further treatment. Investigators should make every effort within the bounds of safety and patient choice to have each patient complete the study. If a patient does not return for a scheduled visit, every effort should be made to contact the patient. In any circumstance, every effort should be made to document patient outcome, if possible. The investigator should inquire about the reason for withdrawal; request the patient return for a final visit, if applicable and follow-up with the patient regarding any unresolved adverse events. As possible, the reason(s) for withdrawal (if given) will be recorded.

If the patient withdraws from the study and also withdraws consent for disclosure of future information, no further evaluations should be performed and no additional data should be collected. The sponsor may retain and continue to use any data collected before such withdrawal of consent.

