8.6. Months 24, 36, 48, 60 and Study Completion or Withdrawal

Patients will return 24, 36, 48 and 60 months (+/- 90 days) post cryoablation procedure or at Study Withdrawal and complete the following assessments:

- ECOG;
- Karnofsky Performance Scale;
- Quality of Life assessments (SF-12);
- CT/MRI Scan, with contrast:
- Safety assessments;
- Assessment of disease progression, including retreatment;
- Assess any new cancer treatment(s).

Patients who request Early Termination from the study will be asked to return for a final visit to complete the above assessments.

Patients may be considered "lost to follow-up" after 3 unsuccessful attempts to contact the patient with on contact being a registered letter to the last known address of the patient. Site should document all attempts to contact the patient in the source documents.

CUC10-LNG06-04 Page 16 of 38

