12.2. Data Processing

To help minimize data entry errors, the EDC system will include real-time edit checks that will identify potential data issues at the time of entry. These edit checks will display on-screen messages when triggered so that the investigator or data entry designee can immediately review the potential data issue and address it before leaving the form.

All eCRFs will be reviewed by clinical staff within Galil Medical to check for completeness and potential unresolved data entry issues. A Galil Medical representative will generate queries within the system for open data issues and follow-up with each site, as necessary, to resolve key data element issues.

The investigator will review all eCRFs created and will approve each patient's eCRFs via electronic signature within the EDC system. The database will be subject to periodic interim analyses based on key study milestones. Prior to each milestone analysis, a Galil Medical representative will work with each site to ensure a data set that is as complete and accurate as possible. At the conclusion of the study, the database will undergo a final review and then be locked. No changes will be allowed in the database after the final lock without the written authorization of the appropriate Galil Medical management team members.

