#### Study Design

This is a prospective single-arm feasibility study designed to determine the safety of Galil Medical's Cryoablation System and needles in cryoablation of lung tumors, as well as give an insight into the efficacy of the treatment. All comparisons will be qualitative in nature. Descriptive results of this feasibility study may be used to generate hypotheses for a pivotal study.

This study is to enroll at least 30, but up to 40, patients who will undergo cryoablation of at least 1 metastatic pulmonary tumor via a Galil Medical cryoablation system using Galil Medical cryoablation needles.

Patients will be screened within 6 weeks of the cryoablation procedure. After the cryoablation procedure visit date, follow-up visits will consist of within 1 Week of the cryoablation procedure and then 1, 3, 6, 12, 24, 36, 48 and 60 months post cryoablation procedure.

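### Deaths are dated exactly but living patients are censored at their last visit, which lowers survival estimates at interim cuts when between-visit deaths are captured

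*SAP*

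**What the plan says.** For overall survival, the SAP's section on disease recurrence or progression says: "Patients who are alive will be censored at the date of the last visit". For disease-specific survival it says: "Patients who are alive will be censored at the date of their last visit". Protocol 11.5.4 gives the same rules.

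Deaths are not tied to visits. Overall survival "will be analyzed as the time in days from cryoablation procedure to death", and these measures "will be analyzed by Kaplan-Meier methodology".

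After Week 1, the SAP (Study Design) sets visits at "1, 3, 6, 12, 24, 36, 48 and 60 months post cryoablation procedure", so the gap is a year from Month 12 onward. Protocol 8.6 gives the late visits a wide window: "24, 36, 48 and 60 months (+/- 90 days) post cryoablation procedure".

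Protocol 12.2 plans analyses before the end of the study: "The database will be subject to periodic interim analyses based on key study milestones". It does not fix their number, timing or data cut-off. Neither document defines a last-known-alive date or requires a vital-status check before an analysis. On patients who withdraw or miss visits, Protocol 6.4 says: "In any circumstance, every effort should be made to document patient outcome, if possible".

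**The concern.** Take two patients, both seen at Month 12 and neither yet at Month 24. One dies in between and the site reports it. That patient stays in the risk set to the day of death and counts as an event. The other is alive throughout but leaves the risk set at Month 12. Being followed past the last visit then depends on dying, which is informative censoring. The risk set is too small when the between-visit deaths occur, each death takes too large a step out of the curve, and estimated survival falls.

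Protocol 5.3 lists survival at fixed months among the other endpoints, and the sample size sections of both documents say the study's estimates will be used to power a pivotal study. A survival rate several points too low at a milestone analysis could carry into that planning.

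**Working it through.** The documents give no survival assumption or power calculation, so there is no planned figure to reproduce. The check is a simulation of the printed rule.

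**Mechanism.** Each death at time t multiplies the Kaplan-Meier curve by 1 − 1/r(t), where r(t) is the number at risk. Under the printed rule, r(t) omits patients alive at t whose last visit was before t, but keeps those who die at or after t and whose deaths are known. So r(t) is too small and the factor too low.

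**Inputs from the documents.** The visit schedule; n = 40, the upper end of the 30 to 40 planned; the two dating rules.

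**Assumptions.** Exponential survival with true 5-year survival of 50% or 30%; uniform accrual over 1.5 years; 10% a year withdrawal; data cuts 2.5 and 3.5 years after the first enrolment. True values follow from S(t) = S(5)^(t/5), for example 0.50^(2/5) = 75.8% and 0.30^(3/5) = 48.6%.

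**Overall survival at a cut, in time not all patients have reached.** Only enrolments in the first 0.5 of 1.5 years, one third, could have reached 2 years at the 2.5-year cut or 3 years at the 3.5-year cut.

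| True 5-year survival | Cut | Estimate | True | All deaths known to the cut | Shortfall | Deaths known only when next visit is due | Shortfall |
|---|---|---|---|---|---|---|---|
| 50% | 2.5 y | 2-year | 75.8% | 65.8% | 10.0 | 75.1% | 0.7 |
| 50% | 3.5 y | 3-year | 66.0% | 57.0% | 9.0 | 65.2% | 0.8 |
| 30% | 2.5 y | 2-year | 61.8% | 49.3% | 12.5 | 60.7% | 1.1 |
| 30% | 3.5 y | 3-year | 48.6% | 38.4% | 10.2 | 47.2% | 1.4 |

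The first set of estimates uses 20,000 simulated trials per scenario and the second 4,000. Independent repeats agreed within 0.3 points. Censoring survivors at the date last known alive gave 75.8%, 66.0%, 61.8% and 48.3%.

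**Times every patient could have reached.** With true 5-year survival of 50% and all deaths known to the cut, 12-month survival at the 2.5-year cut was 86.8% against 87.1%. The 24-month figure at the 3.5-year cut was 75.0% to 75.4% across runs against 75.8%.

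**A second set of assumptions.** Protocol 3.2 cites 1-year survival of 89.4% in a series of metastatic pulmonary tumors. Take that rate, 24-month accrual, no loss to follow-up, all deaths known, and a cut 12 months after the last enrolment. Then 24-month survival is 75.2% under the printed rule and 79.7% with censoring at the cut-off (true 0.894² = 79.9%). With 1-year survival of 75%, an assumption, it is 49.0% against 56.1% (true 0.75² = 56.2%). In these runs the largest gap at a time all patients had reached was 1.2 points (54.7% against 55.9%).

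**Role of visit spacing.** With 1-year survival of 89.4%, 18-month accrual and a cut 12 months after the last enrolment, 24-month survival was 72.2% with the planned visits and 78.5% with 3-monthly visits, against about 80% with cut-off censoring.

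**Final analysis.** With complete follow-up, 60-month survival was 56.9% against 57.2% with cut-off censoring (true 57.1%). In the first set of assumptions, 10% a year withdrawal gave a shortfall of about 1.5 points and 20% a year about 3. These assume that deaths after withdrawal are not captured. If they are captured, the shortfall grows: in the second set, with 18-month accrual and 10% a year lost, 60-month survival was 47.9% against a true 57.1%, compared with 55.2% when they are not captured.

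**The case against.** The strongest reply is that the large figures need every death up to the cut to be known, and the documents do not establish that. Protocol 14 records adverse events only within 30 days of the procedure, and no later procedure for reporting deaths between visits is described. The instruction in Protocol 6.4 to document outcome concerns patients who withdraw or miss a visit, and it covers being alive as much as having died. If deaths are learned only when the next visit falls due, the shortfall is about 1 point. This stands, and it sets the lower end of the range.

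A reader might infer that the rule always lowers survival, or that the bias is large at any milestone analysis. The documents support neither. The effect is an average one and depends on death capture. Milestone timing is unstated, and where all patients could have reached the time point the effect is about 1 point or less. The large figures belong to the tail, where the sampling standard deviation is itself about 12 points.

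Four smaller points also stand:

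- Protocol 12.2 plans a data clean-up with sites before each milestone analysis, although it sets no vital-status rule.
- Protocol 8 allows extra visits when medically needed, so real gaps may be shorter than simulated.
- The fixed-month survival endpoint in Protocol 5.3 is disease-specific survival, while all the figures here are for overall survival.
- These are supportive, descriptive endpoints with no test or decision threshold, so no formal inference is affected.

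None of this removes the asymmetry, which both documents print in full. How far it bites is left to each site's practice in reporting deaths.

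**Conclusion.** The concern holds in a limited form. When deaths between visits are captured, the censoring rule lowers Kaplan-Meier overall survival on average. Disease-specific survival moves in the same direction, by an amount not computed. The effect is concentrated in the part of the curve not yet reached by all patients at an interim cut. Under 1.5-year accrual and 10% a year withdrawal, 2- or 3-year survival there is understated by about 1 point to about 9 to 13 points, depending on how deaths are learned.

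At 60 months in the final analysis the shortfall is near zero with complete follow-up and about 1.5 points with 10% a year withdrawal, provided deaths after withdrawal are not captured. A reader should not infer that the final survival results are seriously biased in general; that would need substantial loss to follow-up together with capture of later deaths. Direction and pattern are firm. The sizes are illustrative, because accrual, milestone timing, withdrawal and death capture are not in the documents. The rule should be changed, but it does not undermine the study.

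**What to change.** In the SAP section on disease recurrence or progression and in Protocol 11.5.4, censor living patients at the date last known alive from any documented contact: a visit, a telephone call, a reply to a registered letter or a record check. For each analysis, set one data cut-off date that applies equally to deaths and survivors, and have sites confirm vital status up to it.

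If vital status cannot be confirmed across the cohort at a cut, limit deaths and survival time in the same way for every patient, for example at the last visit due, and do not read the curve beyond that follow-up. In the second set of assumptions this symmetric rule gave 24-month survival of 79.7% (true 79.9%) and 56.3% (true 56.2%).

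This is a cheap improvement, though not a free one. It costs a short text change, one extra date field and a brief vital-status check by sites before each milestone analysis, alongside the clean-up that Protocol 12.2 already plans. It adds no patients or study visits.
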